### **6.3 Measures to Minimize Bias: Randomization and Blinding**

#### **6.3.1 Intervention Assignment**

Intervention randomization will occur centrally using an IRT system. There are 2 study intervention arms. Participants will be assigned randomly in a 1:1 ratio to MK-7684A or pembrolizumab alone, respectively.

#### **6.3.2 Stratification**

Intervention randomization will be stratified according to the following factors:

1. ECOG performance score (0 versus 1)
2. PD-L1 TPS (1% to 49% versus  $\geq 50\%$ )
3. Geographic Region: East Asia versus Non-East Asia

#### **6.3.3 Blinding**

A double-blinding technique with in-house blinding will be used. MK-7684A and pembrolizumab will be prepared and/or dispensed in a blinded fashion by an unblinded pharmacist or qualified study site personnel so that the blind is maintained. The participant, the investigator, and Sponsor personnel or delegate(s) who are involved in the study intervention administration or clinical evaluation of the participants are unaware of the intervention assignments.

Access to the randomization schedule and unblinded results for presentation of summaries and analyses to the eDMC will be restricted to an unblinded statistician and as needed, an unblinded scientific programmer performing the analysis, who will have no other responsibilities associated with the study. Participant level PD-L1 results will be masked to the site.

See Section 8.1.10 for a description of the method of unblinding a participant during the study should such action be warranted.

### **6.4 Study Intervention Compliance**

If there are interruptions in the study intervention schedule, the details of and reason for any interruption of study intervention will be documented in the participant's medical record.

Refer to Section 6.6.1 for dose modification and toxicity management for irAEs associated with MK-7684A or pembrolizumab and for other allowed dose interruptions of MK-7684A or pembrolizumab.

When participants will be dosed at the site, they will receive study intervention directly from the investigator or designee, under medical supervision. The date and time of each dose administered in the clinic will be recorded in the source documents and recorded in the CRF. The site should ensure and confirm that the study intervention is administered at the correct dose to the assigned study participant.

## 6.5 Concomitant Therapy

Medications or vaccinations specifically prohibited in the exclusion criteria are not allowed during the treatment period. If there is a clinical indication for any medication or vaccination specifically prohibited, discontinuation from study therapy or vaccination may be required. The investigator should discuss any questions regarding this with the Sponsor's Clinical Director. The final decision on any supportive therapy or vaccination rests with the investigator and/or the participant's primary physician. However, the decision to continue the participant on study intervention requires the mutual agreement of the investigator, the Sponsor, and the participant.

Participants are prohibited from receiving the following therapies during the screening and treatment periods of this study:

- Antineoplastic systemic chemotherapy or biological therapy.
- Immunotherapy not specified in this protocol.
- Chemotherapy not specified in this protocol.
- Investigational agents other than pembrolizumab or MK-7684A.
- Radiation therapy for disease control.
- Note: Palliative radiotherapy is permitted for nontarget lesions if considered medically necessary by the treating physician and upon discussion with the Sponsor.
- Live or live-attenuated vaccines within 30 days before the first dose of study intervention and while participating in the study, and for after the last dose of study intervention.  
Note: Killed vaccines are allowed.  
Note: Any licensed COVID-19 vaccine (including for Emergency Use) in a particular country is allowed in the study as long as they are mRNA vaccines, replication incompetent adenoviral vaccines, or inactivated vaccines. These vaccines will be treated just as any other concomitant therapy.
- Investigational vaccines (ie, those not licensed or approved for Emergency Use) are not allowed.
- Systemic glucocorticoids except when used for the following purposes:
  - To modulate symptoms of an AE that is suspected to have an immunologic etiology.
  - As needed for the prevention of emesis.
  - Premedication for IV contrast allergies.
  - Short-term oral or IV use in doses >10 mg/day prednisone equivalent for COPD exacerbations.

- For chronic systemic replacement not to exceed 10 mg/day prednisone equivalent.
- In addition, the following glucocorticoid use is allowed:
  - For topical use or ocular use
  - Intraarticular joint use
  - For inhalation in the management of asthma or COPD

If the investigator determines that a participant requires any of the aforementioned treatments for any reason, study intervention must be discontinued:

All treatments that the investigator considers necessary for a participant's welfare may be administered at the discretion of the investigator in keeping with the community standards of medical care. All concomitant medication will be recorded on the eCRF including all prescription, OTC products, herbal supplements, and IV medications, and fluids. If changes occur during the study period, documentation of drug dosage, frequency, route, and date should also be included on the eCRF.

All concomitant medications received within 30 days prior to the first dose of study intervention and up to 30 days after the last dose of study intervention should be recorded. All concomitant medications administered during SAEs or ECIs are to be recorded. SAEs and ECIs are defined in Section 8.4.

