### **Diagnostic Assessments**

8. Has known active or untreated CNS metastases and/or carcinomatous meningitis. Participants with previously treated brain metastases may participate provided they are radiologically stable (ie, without evidence of progression) for at least 4 weeks by repeat imaging (note: repeat imaging should be performed during study screening), clinically stable, and without requirement of steroid treatment for at least 14 days prior to first dose of study intervention.
9. Has severe hypersensitivity ( $\geq$ Grade 3) to MK-7684A or pembrolizumab and/or any of its excipients.
10. Has an active autoimmune disease that has required systemic treatment in past 2 years (ie, with use of disease modifying agents, corticosteroids, or immunosuppressive drugs). Replacement therapy (eg, thyroxine, insulin, or physiologic corticosteroid replacement therapy for adrenal or pituitary insufficiency) is not considered a form of systemic treatment and is allowed.
11. Has a diagnosis of immunodeficiency or is receiving chronic systemic steroid therapy (in dosing exceeding 10 mg daily of prednisone equivalent) or any other form of immunosuppressive therapy within 7 days prior to the first dose of study intervention.
12. Has a history of (non-infectious) pneumonitis that required steroids or has current pneumonitis.
13. Has a known history of interstitial lung disease. Lymphangitic spread of the NSCLC is not exclusionary.
14. Has an active infection requiring systemic therapy.
15. Has a known history of HIV infection. No HIV testing is required unless mandated by local health authority. See Section 10.7.1 for South Africa-specific requirements.
16. Has a known history of Hepatitis B (defined as HBsAg reactive) or known active Hepatitis C virus (defined as HCV RNA [qualitative] is detected) infection.

Note: No testing for Hepatitis B and Hepatitis C is required unless mandated by local health authority.

17. Has a history or current evidence of any condition, therapy, or laboratory abnormality that prevents the participant from receiving platinum-doublet chemotherapy for first line NSCLC, or that might confound the results of the study, interfere with the participant's participation for the full duration of the study, or is not in the best interest of the participant to participate, in the opinion of the treating investigator.

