### **Restarting Study Interventions:**

Participants may restart pembrolizumab monotherapy, coformulations, or IO combinations as described below:

If the toxicities do resolve and conditions are aligned with what is defined in the Dose Modification and Toxicity Management Guidelines for irAEs, pembrolizumab monotherapy, coformulations, or IO combinations may be restarted at the discretion of the investigator.

Dose Modification and Toxicity Management Guidelines for irAEs associated with pembrolizumab monotherapy, coformulations, or IO combinations are provided in [Table 5](#).

Table 5 Dose Modification and Toxicity Management Guidelines for Immune-related Adverse Events Associated with Pembrolizumab Monotherapy, Coformulations or IO Combinations

General instructions:				
1. Severe and life-threatening irAEs should be treated with IV corticosteroids followed by oral steroids. Other immunosuppressive treatment should begin if the irAEs are not controlled by corticosteroids. 2. Pembrolizumab monotherapy, coformulations or IO combinations must be permanently discontinued if the irAE does not resolve or the corticosteroid dose is not $\leq 10$ mg/day within 12 weeks of the last treatment. 3. The corticosteroid taper should begin when the irAE is $\leq$ Grade 1 and continue at least 4 weeks. 4. If pembrolizumab monotherapy, coformulations or IO combinations have been withheld, treatment may resume after the irAE decreased to $\leq$ Grade 1 after corticosteroid taper.				
irAEs	Toxicity Grade (CTCAE v5.0)	Action With Pembrolizumab Monotherapy, Coformulations or IO Combinations	Corticosteroid and/or Other Therapies	Monitoring and Follow-up
Pneumonitis	Grade 2	Withhold	
 
Administer corticosteroids (initial dose of 1 to 2 mg/kg prednisone or equivalent) followed by taper
 
Add prophylactic antibiotics for opportunistic infections
 
	
 
Monitor participants for signs and symptoms of pneumonitis
 
Evaluate participants with suspected pneumonitis with radiographic imaging and initiate corticosteroid treatment
 

	Recurrent Grade 2, Grade 3 or 4	Permanently discontinue		

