## 7.1 Discontinuation of Study Intervention

Discontinuation of study intervention does not represent withdrawal from the study.

As certain data on clinical events beyond study intervention discontinuation may be important to the study, they must be collected through the participant's last scheduled follow-up, even if the participant has discontinued study intervention. Therefore, all participants who discontinue study intervention before completion of the protocol-specified treatment period will still continue to be monitored in the study and participate in the study visits and procedures as specified in Section 1.3 and Section 8.11.4 unless the participant has withdrawn from the study (see Section 7.2).

Participants may discontinue study intervention at any time for any reason or be discontinued from the study intervention at the discretion of the investigator should any untoward effect occur. In addition, a participant may be discontinued from study intervention by the investigator or the Sponsor if study intervention is inappropriate, the study plan is violated, or for administrative and/or other safety reasons.

A participant must be discontinued from study intervention, but continue to be monitored in the study for any of the following reasons:

- The participant or participant's legally acceptable representative requests to discontinue study intervention.
- Any prolonged interruption of study intervention beyond the permitted periods, for irAE management or other allowed dose interruptions, as noted in Section 6.6.1, require Sponsor consultation prior to restarting treatment. If treatment will not be restarted, the participant will continue to be monitored in the study and the reason for discontinuation of study intervention will be recorded in the medical record.

- The participant has a medical condition or personal circumstance which, in the opinion of the investigator and/or Sponsor, placed the participant at unnecessary risk from continued administration of study intervention.
- The participant has a confirmed positive serum pregnancy test.
- Taking any prohibited medications noted in Section 6.5.
- Radiographic disease progression outlined in Section 8.2.1.5 (after obtaining informed consent addendum and Sponsor communication, the investigator may elect to continue treatment beyond iCRO-verified disease progression).
- Any progression or recurrence of malignancy, or any occurrence of another malignancy that requires active treatment.

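### Section 6.5 makes stopping study drug discretionary in one place and mandatory in another for the same prohibited items, and read with Section 7.1 it can conflict with the immunosuppressant step in Table 5

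*Combined protocol and SAP*

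**What the plan says.** The opening paragraph of Section 6.5 extends the exclusion criteria past entry: "Medications or vaccinations specifically prohibited in the exclusion criteria are not allowed during the treatment period". It then sets a discretionary consequence: "If there is a clinical indication for any medication or vaccination specifically prohibited, discontinuation from study therapy or vaccination may be required". Continuation is left open, since "the decision to continue the participant on study intervention requires the mutual agreement of the investigator, the Sponsor, and the participant".

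A list of prohibited therapies follows. It includes live vaccines and systemic glucocorticoids, the latter with exceptions, one of which is treatment of a suspected immunologic AE. After the list comes a mandatory consequence: "If the investigator determines that a participant requires any of the aforementioned treatments for any reason, study intervention must be discontinued".

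Section 7.1, among the reasons for which study intervention has to be stopped, lists: "Taking any prohibited medications noted in Section 6.5".

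Two further texts bear on immune-related AEs. Exclusion 11 in Section 5.2 bars chronic systemic steroids above a stated dose, or "any other form of immunosuppressive therapy within 7 days prior to the first dose of study intervention". In Section 6.6.1, general instruction 1 of Table 5 says: "Other immunosuppressive treatment should begin if the irAEs are not controlled by corticosteroids". General instruction 4 of that table allows study drug that was withheld to resume once the event has come down to Grade 1 or lower after the steroid taper.

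**The concern.** A stopping rule should give the same answer wherever a site looks it up. Here the opening of Section 6.5 leaves the decision to a three-way agreement, while the end of the section and Section 7.1 leave no choice.

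The second difficulty is that a site following the toxicity table may, on one available reading, be giving a treatment that obliges it to stop study drug, even though the same table provides a way back onto treatment.

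Discontinuation of study intervention due to an AE is a named safety endpoint (Sections 3 and 9.4.2), and exposure is summarised as the number of cycles received (Section 9.12). Where the text does not settle whether a participant stops, both measures partly reflect which sentence was applied. The passages also still matter in practice: Amendment 06 lets some participants stay on pembrolizumab until discontinuation criteria are met and supplies no replacement criteria or concomitant-therapy rule.

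**Working it through.** No plan figure is involved. The check sets the texts side by side for two cases.

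**Case 1: a live vaccine is clinically needed during treatment.**

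1. Exclusion 6 bars live or live-attenuated vaccines before the first dose, so the opening sentence of Section 6.5 applies. Result: discontinuation is possible, and continuation is open by agreement.
2. The Section 6.5 list also names live vaccines and expressly covers the time in the study, so the closing sentence applies. Result: discontinuation is mandatory.
3. Section 7.1 reaches any medication that Section 6.5 prohibits. Result: discontinuation is mandatory.
4. No text says which rule takes precedence.

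This conflict does not depend on exclusion 11 or Table 5.

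**Case 2: first Grade 3 colitis, not controlled by corticosteroids, treated with another immunosuppressant, then recovered to Grade 1 after taper.**

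| Text | Consequence for study drug |
|---|---|
| Table 5, colitis row and instruction 4 | Withheld; may resume, if the 12-week limits in instruction 2 are met |
| Section 6.5 opening, if it carries exclusion 11 forward | Discontinuation possible; continuation by agreement |
| Section 6.5 closing sentence | Unclear: the list just before it does not name non-steroid immunosuppressants |
| Section 7.1, with the carry-over | Mandatory stop |

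The immune-AE exception in Section 6.5 sits under systemic glucocorticoids and does not extend to other immunosuppressants. The conflict in this case therefore runs through two steps only: the carry-over sentence, and then Section 7.1.

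**Where Case 2 makes no difference.** Table 5 already requires permanent discontinuation for, among others, Grade 3 or 4 pneumonitis, hepatic events, nephritis and neurological toxicity, and for Grade 2 to 4 myocarditis. The same holds when the event has not resolved, or the steroid dose has not come down to 10 mg/day or less, within 12 weeks. Those participants stop on any reading.

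**Size.** The documents give no rate for either case. As an assumption only, if 1% to 3% of the 1264 enrolled participants were affected, the count would be 0.01 × 1264 = 12.6 to 0.03 × 1264 = 37.9, or about 13 to 38. That base is everyone enrolled, not those still on treatment.

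**The case against.** The strongest reply is that the protocol, read as a whole, means irAE care to proceed under Section 6.6.1.

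- Section 6.5.1 sends supportive care for immunologic AEs to Section 6.6.1.
- The text after the closing sentence of Section 6.5 permits treatments needed for the participant's welfare.
- Section 7.1 contemplates restarting after an interruption for irAE management and has a separate stop for toxicity.
- Exclusion 11 has its own window of 7 days before the first dose, and it is arguable whether a class barred only at entry counts as specifically prohibited on treatment.
- Continuation needs Sponsor agreement, which limits variation between sites.
- The closing sentence ends in a colon with nothing after it, so text may have been lost in extraction.

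Much of this stands, and it narrows the point. A reader might infer that the closing sentence of Section 6.5 by itself forces the colitis participant off study drug. The text does not establish that, because its most natural reference is the list before it. But none of these passages exempts a Table 5 immunosuppressant from the prohibition or from the Section 7.1 stop; they support giving the treatment and are silent on its consequence. The Section 6.5.1 pointer also names Table 4, which is the study-interventions table in Section 6.1, whereas the irAE guidance is Table 5. And none of the replies touches Case 1.

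**Conclusion.** The wording is wrong as it stands, within limits. For items that are both exclusion-listed and on the Section 6.5 list, the plan states a discretionary and a mandatory consequence with no precedence. For non-steroid immunosuppressants given under Table 5, the conflict is conditional: it assumes that the carry-over sentence extends exclusion 11 into treatment, and it affects only withhold-and-resume events.

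Three stronger readings might be inferred and are not supported:

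- That the two consequences are opposites. One is discretionary and the other mandatory.
- That every participant given an immunosuppressant beyond steroids is affected. Table 5 already stops many of them.
- That the trial's efficacy result is biased by arm. OS is analysed by ITT from randomization to death, and how a stop is classified does not enter it. Any difference by arm in AE discontinuations would need unequal rates of these events, which the documents do not give. Under Amendment 06 the second interim and final analyses are cancelled and MK-7684A recipients move to pembrolizumab.

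What remains is a contradictory stopping rule for participants still on pembrolizumab, and some ambiguity in the end-of-study safety and exposure summaries. The vaccine case bears mainly on exposure; the immunosuppressant case bears on both exposure and AE discontinuations.

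**What to change.** Reconcile four texts: Section 6.5 (opening paragraph and closing sentence), Section 7.1, exclusion 11 as carried into treatment, and Table 5 in Section 6.6.1. The revised wording should:

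- attach one consequence to each prohibited class and use it in both Section 6.5 and Section 7.1;
- define which items the closing sentence of Section 6.5 covers, so that it does not reach the permitted exceptions in the list;
- state whether immunosuppressants given under Table 5 are inside or outside the prohibition, and align the resumption provision accordingly;
- correct the table reference in Section 6.5.1.

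Which rule applies is for the sponsor to decide. The cost is wording in these sections and a clarification letter to sites, with no new procedures or data. For the end-of-study summaries, it would help to list any participants whose discontinuation followed a Section 6.5 medication, with the recorded reason; this uses data already collected.

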### **6.5.1 Rescue Medications and Supportive Care**

Participants should receive appropriate supportive care measures as deemed necessary by the treating investigator.

Suggested supportive care measures for the management of AEs with potential immunologic etiology are outlined along with the dose modification guidelines in Section 6.6.1.

Note: If after the evaluation of the event, it is determined not to be related to pembrolizumab or MK-7684A, the investigator does not need to follow the treatment guidance. Refer to [Table 4](#) in Section 6.6.1 for guidelines regarding dose modification and supportive care.

## **6.6 Dose Modification (Escalation/Titration/Other)**

### **6.6.1 Immune-Related Events and Dose Modification (Withhold, Treat, Discontinue)**

#### **Dose Modification and Toxicity Management for Immune-related AEs Associated with Pembrolizumab Monotherapy, Coformulations or IO Combinations**

AEs associated with pembrolizumab monotherapy, coformulation, or IO combination exposure may represent an immune-related response. These irAEs may occur shortly after the first dose or several months after the last dose of pembrolizumab monotherapy, coformulation, or IO combination treatment and may affect more than one body system simultaneously. Therefore, early recognition and initiation of treatment is critical to reduce

complications. Based on existing clinical study data, most irAEs were reversible and could be managed with interruptions of pembrolizumab monotherapy, coformulation, or IO combination administration of corticosteroids and/or other supportive care. For suspected irAEs, ensure adequate evaluation to confirm etiology or exclude other causes. Additional procedures or tests such as bronchoscopy, endoscopy, skin biopsy may be included as part of the evaluation.

### **Attribution of Toxicity:**

When study interventions are administered in combination, attribution of an adverse event to a single component is likely to be difficult. Therefore, while the investigator may attribute a toxicity event to pembrolizumab monotherapy, coformulations, or IO combinations, pembrolizumab monotherapy, coformulations, or IO combinations must be held according to the criteria in the Dose Modification and Toxicity Management Guidelines for Immune-Related Adverse Events.

